6.3.4.1. Time window for recording concomitant medication/vaccination in the CRF

All concomitant medications, with the exception of vitamins and/or dietary supplements, administered at any time during the period starting with the administration of *Fluarix Tetra* and ending 21 days (Day 0 to Day 20) after vaccination must be recorded in the CRF.

Any vaccine not foreseen in the drug use investigation protocol administered in the period beginning 21 days (Day -20 to Day 0) preceding the dose of *Fluarix Tetra* and ending 21 days (Day 0 to Day 20) after the dose of *Fluarix Tetra* must be recorded in the CRF.

Any investigational medication or vaccine administered throughout the drug use investigation (i.e. from 21 days before the first dose of the vaccine and 21 days after administration of the dose of the vaccine) must be recorded in the CRF.

6.4. Outline of study procedures

Table 1 presents the list of drug use investigation procedures.

Table 1 List of study procedures

Type of contact	Enrolment **	Follow-up contact 21 days after vaccination **
Informed consent ¹	●	
Check inclusion/exclusion criteria	●	
Demographic data	●	
Medical history	●	
Vaccination history *	●	
Physical examination	●	
Pre-vaccination body temperature	●	
Record vaccination information	●	
Distribution of diary cards	○	
Record AEs within 21 days (Day 0 to Day 20) post-vaccination, by physician	●	●
Return of diary cards ^a		○
Diary card transcription by physician		●
Record concomitant medication/vaccination	●	●
Reporting of ADRs	●	●
Reporting of SAEs	●	●
Drug use investigation conclusion		●

● is used to indicate a study procedure that requires documentation in the individual CRF.

○ is used to indicate a study procedure that does not require documentation in the individual CRF.

¹Informed consent for participation into the drug use investigation can be taken after vaccination. The vaccination procedure is not part of the drug use investigation.

* Vaccination history is influenza vaccine history within the three previous seasons.

^a The subject/subject's parent(s)/LAR(s) will be instructed to return the completed diary card to the physician or phone or mail, to report any AEs/ADRs/SAEs during the 21 days (Day 0 to Day 20) using diary cards after *Fluarix Tetra* is administered.

^{**} Subjects who are pregnant and receive *Fluarix Tetra* or subjects who become pregnant within 21 days after receiving *Fluarix Tetra* should report to/notify GSK, if possible. Pregnancy outcome in vaccinated pregnant subjects will be followed-up at 6-8 weeks after delivery, if possible.

6.5. Detailed description of study procedures

6.5.1. Procedures prior to study participation

6.5.1.1. Informed consent

The ICF/IAF for this drug use investigation is for the collection and handling of personal and safety information after vaccination with *Fluarix Tetra*. Diary cards will be used to collect safety information and for SDV. The ICF/IAF for this drug use investigation will not include consent for vaccination as vaccination is at the discretion of the subject/subject's parent(s)/LAR(s) and the physician. Informed consent may be taken after the vaccination. Parent(s)/LAR(s) who agree to have their eligible children participate in this drug use investigation will return the diary card to physician and accept a telephone interview from physicians for collection of safety information. Information collected will be treated confidentially and for the purpose of reporting SAE(s) to KIDS, and for public disclosure, if required.

Before performing any other study procedure, the signed informed consent as ICF/IAF of the subject/subject's parent(s)/LAR(s) must be obtained.

6.5.2. Procedures related to vaccination and outside the drug use investigation

6.5.2.1. Contraindications, warnings, and precautions to vaccination

Contraindications, warnings, and precautions to vaccination are to be checked at the beginning of each vaccination visit (see Sections [6.3.2](#) and [6.3.3](#)).

6.5.2.2. Pre-vaccination body temperature

The body (oral, axillary or tympanic) temperature of all subjects needs to be measured prior to *Fluarix Tetra* administration. The preferred route for recording temperature in this drug use investigation will be oral/axillary/tympanic depending on the age of enrolled vaccinees. . If the subject has fever [fever is defined as temperature ≥ 37.5 °C (99.5 °F) on oral, axillary or tympanic setting on the day of vaccination, the vaccination visit will be rescheduled.

6.5.2.3. Vaccination

- After completing the prerequisite procedures prior to vaccination, *Fluarix Tetra* will be administered according to the PI (refer to Section [6.3.1.2](#) for description of the vaccine administration procedure). If the physician or delegate determines that the

subject's health on the day of vaccination temporarily precludes vaccination, the visit will be rescheduled.

- The vaccinees will be observed closely for at least 30 minutes, with appropriate medical treatment readily available in case of anaphylaxis following the administration of *Fluarix Tetra*.

6.5.3. Procedures during the study

6.5.3.1. Check inclusion and exclusion criteria

Check all applicable inclusion and exclusion criteria as described in Sections 4.2 and 4.3 before enrolment.

6.5.3.2. Demographic data

Record demographic data such as age, height, weight, gender, and ethnicity in the subject's CRF.

6.5.3.3. Medical history

Perform a history-directed medical examination and record any significant pre-existing conditions or signs and/or symptoms present judged by physicians in a subject prior to the start of the drug use investigation in the CRF. Treatment of any abnormality observed during this examination has to be performed according to local medical practice outside this drug use investigation or by referral to an appropriate health care provider.

6.5.3.4. Vaccination history

Influenza vaccine history within the three previous seasons must be recorded in the CRF. And collect information regarding all vaccines not foreseen in the protocol administered to the subject 21 days (Day -20 to Day 0) prior to vaccination with *Fluarix Tetra*.

6.5.3.5. Physical examination

Perform a physical examination of the subject. Collected information needs to be recorded in the CRF.

6.5.3.6. Reproductive history (Only for Pregnant Subjects)

Once the physician becomes aware of a pregnancy, the reproductive history of the pregnant subject will be collected and recorded in the CRF.

6.5.3.7. Record concomitant medication/vaccination

Concomitant medication/vaccination must be recorded in the CRF (see Section 6.3.4).

6.5.3.8. Distribution, return, and transcription of diary cards

The physician will provide the diary card to the subject/subject's parent(s)/LAR(s) to record e.g. medication taken until the next visit/contact. The subject/subject's

parent(s)/LAR(s) will be instructed to return the completed diary card to the physician at the next visit/contact.

- Collection and verification of the completed diary card will take place during discussion with the subject/subject's parent(s)/LAR(s) at the subsequent visit/contact. Any unreturned diary cards will be sought from the subjects through telephone call(s) or any other convenient procedure. The physician will transcribe the collected information into the CRF in English.
- Collection of pregnancy outcome information from pregnant subjects who received *Fluarix Tetra*, at 6-8 weeks after the EDD, if possible.

6.5.3.9. Record AEs, ADRs and SAEs

- The subject/subjects' parent(s)/LAR(s) will be instructed to contact the physician immediately should the subjects manifest any signs or symptoms they perceive as serious.
- Refer to Section [7.2](#) for procedures for the physician to record AEs, ADRs and SAEs and to Section [7.3](#) for guidelines on how to report these **ADRs/SAEs** to GSK Vaccines.
- After vaccination, diary cards will be provided to the subjects to record body (oral/axillary/tympanic) temperature and any AEs (i.e. on the day of vaccination and during the next 20 days) occurring after vaccination. The subject/subject's parent(s)/LAR(s) will be instructed to return the completed diary card to the physician on their next drug use investigation visit or provide details during the phone or by postal mail.

6.5.3.10. Procedures during follow-up visits/contacts for AEs/ ADRs /SAEs

Note that some of the procedures to be performed during the follow-up visits/contacts (record AEs) are described in Section [6.5.3.6](#) up to Section [6.5.3.9](#).

- Collection and verification of completed diary card during discussion with the subject/subject's parent(s)/LAR(s) at the subsequent visit/contact. Any unreturned diary cards will be sought from the subjects through telephone call(s) or any other convenient procedure. The physician will transcribe the collected information into the CRF in English.
- Checking for pregnancy within 21 days after *Fluarix Tetra* vaccination, if possible.

6.5.3.11. Study conclusion

The physician will review safety data collected to ensure accuracy and completeness and will complete the drug use investigation conclusion page in the CRF.

7. ADVERSE EVENTS AND SERIOUS ADVERSE EVENTS

The physician or site staff is/are responsible during the drug use investigation for the detection and documentation of events meeting the criteria and definition of an AE, **ADR** and a SAE as provided in this protocol.

Each subject/subject's parent(s)/LAR(s) will be instructed to contact the physician immediately should the subject manifests any signs or symptoms they perceive as serious.

7.1. Safety definitions

7.1.1. Definition of an adverse event

An AE is any untoward medical occurrence in a subject, temporally associated with the use of a medicinal product, whether or not considered related to the medicinal product.

An AE can therefore be any unfavourable and unintended sign (including an abnormal laboratory finding), symptom, or disease (new or exacerbated) temporally associated with the use of a medicinal product. For marketed medicinal products, this also includes failure to produce expected benefits (i.e. lack of efficacy), abuse or misuse.

Examples of included AE:

- Significant or unexpected worsening or exacerbation of the condition.
- Exacerbation of a chronic or intermittent pre-existing condition including either an increase in frequency and/or intensity of the condition.
- New conditions detected or diagnosed after *Fluarix Tetra* administration even though they may have been present prior to the start of the drug use investigation.
- Signs, symptoms, or the clinical sequelae of a suspected interaction.
- Signs, symptoms, or the clinical sequelae of a suspected overdose of a concurrent medication (overdose per se should not be reported as an AE/SAE).
- Signs, symptoms temporally associated with vaccine administration.
- Significant failure of expected pharmacological or biological action.

Examples of AE (DO NOT include):

- Medical or surgical procedures (e.g. endoscopy, appendectomy); the condition that leads to the procedure is an AE.
- Situations where an untoward medical occurrence did not occur (e.g. social and/or convenience admission to a hospital, admission for routine examination).
- Anticipated day-to-day fluctuations of pre-existing disease(s) or condition(s) present or detected at the start of the drug use investigation that do not worsen.

NB. AEs to be recorded as expected AEs are described in Section **Error! Reference source not found.** All other AEs will be recorded as unexpected AEs.

Example of events to be recorded in the medical history section of the CRF:

- Pre-existing conditions or signs and/or symptoms present in a subject prior to the start of the drug use investigation (i.e. prior to the first study vaccination).

7.1.2. Definition of adverse drug reaction

Adverse drug reaction (ADR) represents adverse, unintended reactions from normal administration/use of the pharmaceuticals, etc. for which the causal relationship with the particular pharmaceutical cannot be excluded. Of the voluntarily reported adverse events, those with no known causal relationship with the pharmaceutical are deemed to be adverse drug reactions.

7.1.3. Definition of a serious adverse event

A SAE is any AE that:

- a. Results in death.
- b. Is life-threatening.

NB: The term 'life-threatening' in the definition of 'serious' refers to an event in which the subject was at risk of death at the time of the event. It does not refer to an event, which hypothetically might have caused death, had it been more severe.

- c. Requires hospitalisation or prolongation of existing hospitalisation.

NB: In general, hospitalisation signifies that the subject has been admitted at the hospital or emergency ward for observation and/or treatment that would not have been appropriate in the physician's office or out-patient setting.

Complications that occur during hospitalisation are also considered AEs. If a complication prolongs hospitalisation or fulfils any other serious criteria, the event will also be considered serious. When in doubt as to whether 'hospitalisation' occurred or was necessary, the AE should be considered serious.

Hospitalisation for elective treatment of a pre-existing condition (known/diagnosed prior to informed consent signature) that did not worsen from baseline is not considered an SAE.

- d. Results in disability/incapacity, or

NB: The term disability means a substantial disruption of a person's ability to conduct normal life functions. This definition is not intended to include experiences of relatively minor medical significance such as uncomplicated headache, nausea, vomiting, diarrhoea, influenza like illness, and accidental trauma (e.g. sprained ankle) which may interfere or prevent everyday life functions but do not constitute a substantial disruption.

- e. Is a congenital anomaly/birth defect in the offspring of a study subject.

Medical or scientific judgement should be exercised in deciding whether reporting is appropriate in other situations, such as important medical events that may not be immediately life-threatening or result in death or hospitalisation but may jeopardise the subject or may require medical or surgical intervention to prevent one of the other outcomes listed in the above definition. These should also be considered serious. Examples of such events are invasive or malignant cancers, intensive treatment in an emergency

room or at home for allergic bronchospasm, blood dyscrasias, or convulsions that do not result in hospitalisation.

7.1.4. *Pregnancy*

Any eligible pregnant female for whom the participating physician has decided to administer *Fluarix Tetra* vaccine may be enrolled in the drug use investigation after the subject has signed the ICF/IAF. If the participating physician becomes aware of a pregnancy during the course of the 21 days follow-up of his/her female subjects, he/she has to notify GSK using the Pregnancy Notification form within 2 weeks, if possible.

All pregnant subjects in the drug use investigation will be followed up to 6-8 weeks after delivery for outcome of pregnancy, if possible.

While pregnancy itself is not considered an AE or SAE, any pregnancy complication or elective termination of a pregnancy for medical reasons will be recorded and reported as an AE or a SAE, as described in Section 7.1.1 and 7.1.3, and will be followed, if possible, as described in Section 7.4.1.

7.1.5. *Clinical laboratory parameters and other abnormal assessments qualifying as adverse events or serious adverse events*

Abnormal laboratory findings (e.g. clinical chemistry, haematology, urinalysis) or other abnormal assessments that are judged by the physician to be clinically significant will be recorded as AEs or SAEs if they meet the definition of an AE, as defined in section 7.1.1, or of an SAE, as defined in Section 7.1.3. Clinically significant abnormal laboratory findings or other abnormal assessments that are detected during the drug use investigation or are present at baseline and significantly worsen following the start of the study will be reported as AEs or SAEs. However, clinically significant abnormal laboratory findings or other abnormal assessments that are associated with the disease being studied, unless judged by the physician as more severe than expected for the subject's condition, or that are present or detected at the start of the drug use investigation and do not worsen, will not be reported as AEs or SAEs.

The physician will exercise his or her medical and scientific judgement in deciding whether an abnormal laboratory finding or other abnormal assessment is clinically significant.

7.2. Detecting and recording adverse events, adverse drug reactions, serious adverse events, and pregnancies

7.2.1. Time period for detecting and recording adverse events, adverse drug reactions serious adverse events, and pregnancies

All AEs, ADRs and SAEs starting immediately following administration of *Fluarix Tetra* must be recorded onto the CRF and all ADRs and SAEs must be reported using the ADR reporting form and SAE reporting form, the latter to be sent to GSK according to the

required timelines, irrespective of intensity or whether or not they are considered vaccination-related.

The standard time period for collecting and recording SAEs will begin at the receipt of *Fluarix Tetra* in the drug use investigation and will end 21 days following administration of *Fluarix Tetra* for each subject. See Section 7.3 for instructions on recording and reporting SAEs.

An overview of the protocol-required reporting periods for AEs, ADRs, SAEs and pregnancies is given in

Table 2.

Table 2 Reporting periods for adverse events, adverse drug reaction, serious adverse events, and pregnancies

Drug use investigation activity	Vaccination	21 days (Day 0 to Day 20) post-vaccination
Reporting of AEs (expected & unexpected)	●	●
Reporting of ADRs	●	●
Reporting of SAEs	●	●
Reporting of pregnancies *	●	●

* Subjects who are pregnant and receive *Fluarix Tetra* or subjects who become pregnant within 21 days after receiving *Fluarix Tetra* in the drug use investigation, the pregnancy outcome (whether full-term or premature, information on the status of the mother and child) of these subjects will be followed-up for 6-8 weeks after delivery, if possible.

Note: Post-vaccination AEs will be collected and reported only for *Fluarix Tetra* received under the drug use investigation procedure (after signing the ICF/IAF).

All AEs/ADRs/SAEs reported within 21 days (Day 0 to Day 20) of administration of *Fluarix Tetra* within the drug use investigation need to be recorded in the CRF. These AEs/ADRs/SAEs will be classified as expected/unexpected at the time of statistical analyses (refer to [GLOSSARY OF TERMS](#) for definitions of expected/unexpected AEs).

Note: Assessment of causality and outcome will be performed by the physician according to the following classification. Causality will be assessed as: Certain; Probable/Likely; Possible; Not-Related; Conditional/ Unclassified; Unassessable/Unclassifiable. Outcome will be assessed as recovered; not recovered; recovering; resolved with sequelae; fatal; unknown.

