7.3. Reporting of serious adverse events, adverse drug reactions and pregnancies

7.3.1. Prompt reporting of serious adverse events and other events to GSK Vaccines

SAEs will be reported promptly to GSK as described in [Table 3](#) once the physician determines that the event meets the protocol definition of an SAE.

ADRs will be reported promptly to GSK as described in [Table 3](#), if possible, once the physician becomes aware of an ADR.

Pregnancies will be reported promptly to GSK as described in [Table 3](#) once the physician becomes aware of a pregnancy in the time period defined in Section [7.2.1](#), if possible. The subject will be followed to determine the outcome of the pregnancy, if possible.

At the end of the pregnancy, whether that be full-term or premature, information on the status of the mother and child will be forwarded to GSK, if possible. Generally, follow-up should be no longer than 6 to 8 weeks following the EDD, if possible.

Table 3 Time frames for submitting SAEs and other event reports related to GSK Vaccines

Type of Event	Initial Report		Follow-up of Relevant Information on a Previous Report	
	Time Frame	Documents	Time Frame	Documents
All SAEs	24 hours *	SAE Report Form	24 hours *	SAE Report Form
All ADRs	5 days **	ADR Report Form	5 days **	ADR Report Form
Pregnancies	2 weeks *	Pregnancy Report Form	2 weeks *	Pregnancy Report Form

* Time frame is allowed after receipt or awareness of the information.

** Recommended Time frame for ADR reporting for the investigators after the awareness of the information.

7.3.2. Contact information for reporting serious adverse events and other events to GSK Vaccines

Contact for Reporting SAEs, ADRs and Pregnancies	
Please see the Local PMS Contact Information for contact details.	
Back-up Contact for Reporting SAEs, ADRs and Pregnancies	
GSK Vaccines Clinical Safety & Pharmacovigilance	[contact] or [contact] email: [contact]
GSK Korea	[contact] or [name]
DreamCIS	[contact]
24/24 hours and 7/7 days availability	

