7.3.5. Completion and transmission of pregnancy reports to GSK Vaccines

Once the physician becomes aware that a subject is pregnant, the physician (or designee) must complete a Pregnancy Report Form and fax or e-mail it to the Contact for Reporting SAEs, ADRs and Pregnancies (refer to the Sponsor Information Sheet) within 2 weeks, if possible.

The Pregnancy Report Form will always be completed as thoroughly as possible with all available details and then dated and signed by the physician (or designee), if possible. Even if the physician does not have all information regarding the pregnancy, the form should still be completed and forwarded to GSK within 2 weeks, if possible. Once additional relevant information is received, the form will be updated and forwarded to GSK within 2 weeks, if possible.

In absence/dysfunction of facsimile equipment, the Contact for Reporting SAEs, ADRs and Pregnancies should be notified by telephone within 2 weeks, if possible. As soon as the facsimile equipment is working again, the physician (or designee) must fax the Pregnancy Report Form to the Contact for Reporting SAEs, ADRs and Pregnancies (refer to the Sponsor Information Sheet) within 2 weeks, if possible.

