9. SUBJECT COMPLETION AND WITHDRAWAL

9.1. Subject completion

A subject who is available for the concluding follow-up contact 21 days after receiving *Fluarix Tetra* is considered to have completed the drug use investigation.

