10.5.2.1. Within group assessment

The AEs/***ADRs/SAEs*** will be analysed in the drug use investigation report according to the expectedness and unexpectedness criteria (Refer to ***GLOSSARY OF TERMS*** for the definitions of expected AEs and unexpected AEs).

The number and percentage, with exact 95% CI, of any AEs, ADRs ***and SAEs*** occurring within 21 days (Day 0 to Day 20) will be tabulated for the number of subjects receiving *Fluarix Tetra*.

The verbatim reports of signs and symptoms will be matched and coded according to the appropriate WHOART PT. The drug use investigation physician will review and confirm the appropriate WHOART PT by responding to data queries if any discrepancies are reported while coding. The percentage of subjects with AEs, ADRs, and ***SAEs*** occurring within 21 days (Day 0 to Day 20) with its exact 95% CI will be tabulated by PT.

The outcome of pregnancy (reported in the pregnancy report form) for subjects who were pregnant at the time of vaccination and those who become pregnant within 21 days after vaccination will be presented, if possible.

SAEs reported during the drug use investigation period [each subject receiving the vaccine up to 21 days (Day 0 to Day 20) after vaccination and for pregnant subjects until 6-8 weeks after delivery] will be described in detail, if possible.

The incidence proportion of AEs as overall and by age group and gender will be measured with the exact 95% CI. An exploratory comparison between these groups will be performed using Chi-square exact test with the statistical significance level 0.05.

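### Two notification clauses limit pregnancy reporting to what the physician learns within 21 days, while follow-up and analysis cover pregnancies that begin within 21 days, so later-recognised ones may be lost

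*Protocol*

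**What the plan says.** **Clauses tied to awareness.** Protocol 7.1.4 has the physician notify the sponsor "If the participating physician becomes aware of a pregnancy during the course of the 21 days follow-up of his/her female subjects". Section 7.3.1 requires prompt reporting "once the physician becomes aware of a pregnancy in the time period defined in Section" 7.2.1, and Table 2 in 7.2.1 gives that period as vaccination plus Day 0 to Day 20.

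**Clauses tied to when the pregnancy begins.** The Synopsis, Section 3 and the Table 2 footnote follow subjects who are pregnant when vaccinated or who become pregnant within 21 days. The Table 2 footnote adds that the pregnancy outcome "of these subjects will be followed-up for 6-8 weeks after delivery, if possible". Section 10.5.2.1 uses the same definition for analysis: outcomes of women pregnant at vaccination and of "those who become pregnant within 21 days after vaccination will be presented, if possible".

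**Clauses with no deadline for awareness.** Section 7.3.5 states: "Once the physician becomes aware that a subject is pregnant, the physician (or designee) must complete a Pregnancy Report Form". Section 6.5.3.6 has reproductive history recorded once the physician becomes aware. The Table 1 footnote says that subjects who become pregnant within 21 days "should report to/notify GSK, if possible".

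**Contacts.** The one active enquiry, in 6.5.3.10, is "Checking for pregnancy within 21 days after" vaccination, if possible, and no test is specified. Section 9.1 regards as having completed the study "A subject who is available for the concluding follow-up contact 21 days after receiving" the vaccine.

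**SAP.** Section 6 lists a pregnancy report analysis for the final report only, if data are collected. It gives no rule for which pregnancies enter.

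**The concern.** The date a pregnancy begins and the date the physician learns of it are different things, and the protocol attaches the same 21 days to each in different places. A woman who conceives late in the window and finds out after her concluding contact meets the definition in 10.5.2.1 but not the trigger in 7.1.4. A site working from 7.1.4 and 7.3.1 could leave her out, while a site working from 7.3.5 would send a form. The same case would be handled differently across centres.

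At stake is the completeness of the pregnancy-outcome presentation for exposures around conception. There is a link to serious events as well. Section 7.1.3 makes a congenital anomaly in a subject's offspring an SAE, and 10.5.2.1 promises a detailed description of SAEs in pregnant subjects until 6 to 8 weeks after delivery. A pregnancy that is never identified contributes nothing to either. If few or no post-vaccination conceptions are listed, a reader may take this to mean that none occurred.

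**Working it through.** The documents state no number of pregnancies, detection rate or recognition lag, so there is no planned figure to reproduce. The check has two parts.

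**1. One case against each clause.** Take a conception on Day 18 that is recognised after the concluding contact.

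| Place in the protocol | What decides | Is the case covered? |
|---|---|---|
| 7.1.4 | Physician aware during the 21-day follow-up | No |
| 7.3.1 (natural reading) | Physician aware in the 7.2.1 period | No |
| 6.5.3.10 | Check at the follow-up contact | Not found |
| 6.5.3.6 | Physician aware, no limit | Yes, if told |
| 7.3.5 | Physician aware, no limit | Yes, if told |
| Table 1 footnote | Became pregnant within 21 days | Yes, if the subject reports |
| Synopsis, Section 3, Table 2 footnote | Became pregnant within 21 days | Yes |
| 10.5.2.1 | Became pregnant within 21 days | Yes |

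The follow-up to 6 to 8 weeks after delivery cannot find this case, because it starts only once a pregnancy is known. The contact after a second dose does not help either, since second doses are for previously unvaccinated children under 9 years.

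**2. How large the gap could be.** Assumptions, neither of them in the documents: conception is equally likely on each of the 21 days (Day 0 to Day 20), and recognition follows L days later. A conception on day d is recognisable by Day 20 if d + L ≤ 20, so the share is (21 − L)/21, and 0 once L reaches 21.

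| Assumed lag L (days) | Recognisable by Day 20 | Recognised later |
|---|---|---|
| 7 | 14/21 = 67% | 33% |
| 10.5 | 10.5/21 = 50% | 50% |
| 14 | 7/21 = 33% | 67% |
| 18 | 3/21 = 14% | 86% |
| 21 or more | 0% | 100% |

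The share recognised later passes one half when L exceeds 10.5 days. If the contact falls on Day 21, the numerator gains one day: at L = 14 the share recognisable is 8/21 = 38%.

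**The case against.** A reader might infer that the protocol reports pregnancies solely when they become known within 21 days. The documents do not support that. Section 7.3.5, which governs pregnancy reports, has no awareness limit. Nor do 6.5.3.6 and the Table 1 footnote. Section 7.1.4 does not say that later-recognised pregnancies go unreported, and its next paragraph covers all pregnant subjects. The wording of 7.3.1 can also be read with the period attached to the pregnancy rather than to the awareness, which would agree with the Table 2 footnote. All of this stands, and it makes the text contradictory rather than closed at 21 days. It does not remove the gap: the open routes depend on someone volunteering the information, and nothing schedules a later enquiry.

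A reader might also infer that most pregnancies beginning in the window cannot yet be known at the contact. That depends on a lag the documents do not give. It holds above 10.5 days and fails below. The contact has no stated latest date, and unreturned diary cards are pursued by telephone, so some contacts may come later and find more.

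Finally, the output is minor. Pregnancy outcome is not an endpoint in 10.1, is presented if possible, and involves no planned rate or comparison. SAP 6.2 marks pregnancy as not applicable to the 6-35 month group, which is 720 of the maximum 1,440, and the other 720 include children and older adults. This also stands, and it limits the weight of the point. Women already known to be pregnant at vaccination are not affected.

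**Conclusion.** The inconsistency is real. Section 7.1.4, and 7.3.1 on its natural reading, set a narrower reporting trigger than the population that the Synopsis, Section 3, the Table 2 footnote and 10.5.2.1 say will be followed and analysed. Sections 6.5.3.6 and 7.3.5 and the Table 1 footnote set no deadline. Pregnancies that begin in the window and are recognised after the last contact may therefore go unreported at some sites, and no planned step looks for them.

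The share at risk is unknown. Under uniform conception it runs from one third at a 7-day lag to all at 21 days or more. The absolute number is probably small, and the documents do not state how many women of child-bearing age will enrol. The AE and SAE endpoints for Day 0 to Day 20 are unaffected. The change is worth making because it costs little and could recover exposures around conception that a site may otherwise omit.

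**What to change.** - **Reporting clauses.** Reconcile 7.1.4 and 7.3.1 with 6.5.3.6, 7.3.5, 10.5.2.1 and the Table 1 footnote, so that the 21 days define the exposure (pregnant at vaccination, or conception on Day 0 to Day 20) and not the date of awareness. This brings the reporting rule into line with the plan's own analysis definition and leaves vaccination and care unchanged.
- **Existing contact.** At the 21-day contact, remind the subject to tell the site if a pregnancy dating from this period is recognised later. No new contact is needed.
- **Analysis.** In 10.5.2.1 and the SAP pregnancy analysis, decide inclusion by the conception date derived from the estimated delivery date, and list the two groups separately (pregnant at vaccination; conceived on Day 0 to Day 20).
- **Reporting of results.** State that pregnancies recognised after the last contact are ascertained passively, so that an empty row is not read as none.

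The cost is a few words in the protocol and SAP, one sentence at the contact, and a few later pregnancy forms. Capture will still depend partly on subjects reporting back.
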